## 1.2.4 Trial Plan

Treatment of oral GVHD by topical agents is an appealing strategy because it would potentially avoid the adverse effects associated with systemic immunosuppression and reduce systemic exposure to glucocorticoids. Most importantly, using immunosuppressive agents locally would concentrate the treatment effects for potential maximum benefit. Conversely, use of systemic

agents for the same purpose would interfere not only with the undesirable GVH response, but also with immune responses directed against the malignancy (the graft vs. tumor effect), which is the principal mechanism through which reduced intensity transplants achieve sustained disease remission.

Therefore, we propose this pilot randomized double blind placebo controlled trial of topical clobetasol 0.05% oral rinse for oral cGVHD. Consenting subjects with clinically significant oral cGVHD will be randomized to receive clobetasol or placebo oral rinse for 2 weeks. All subjects will be evaluated biweekly. Clinically significant oral cGVHD is defined as a score of 20 or greater on the Oral Mucositis Rating Scale (OMRS) based on the patient cohort (over 250) seen in the NIH natural history of cGVHD protocol. At the first 2 week appointment, patients will be unblinded and subjects randomized to placebo will be assigned to additional 2-4 week open label treatment period with topical clobetasol rinse. All patients will therefore complete 4 weeks of treatment with the study drug (2 additional weeks for patients originally assigned to clobetasol arm and 4 weeks for patients assigned to placebo arm). All patients will be reevaluated 1 month following the open label period to evaluate the response and collect follow-up data.

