## 3.5 QUESTIONNAIRES

## 3.5.1 Oral Mucositis Rating Scale

Description. The OMRS was constructed through the careful selection of clinical descriptors of oral mucosal changes related to GVHD and also related to BMT. The OMRS was developed "...as a research tool for the comprehensive measurement of a broad range of oral tissue changes associated with cancer therapy" and "to develop an index for assessing acute oral mucositis after BMT". Preliminary development of this scale was performed in studies of chemotherapy toxicities and cGVHD and use of the tool allowed "expedient, efficient, detailed, and reproducible classification of oral changes". The OMRS was used by Schubert, Sullivan, Morton et al. (1984) with 60 patients, who were 180 to 500 days after ABMT, to determine if late oral abnormalities were associated with the presence of cGVHD. Oral manifestations found to be most strongly associated with cGVHD included atrophy and erythema or lichenoid lesions of the buccal and labial mucosa and oral pain.

The tool divides the oral cavity into seven distinct anatomic areas: lips; labial and buccal mucosa; tongue; floor of mouth; palate; and attached gingiva. Each site is further divided into upper and lower (lips and labial mucosa), right and left (buccal mucosa), dorsal, ventral, and lateral (tongue), and hard and soft (palate). Descriptive categories include atrophy, pseudomembrane, erythema, hyperkeratosis, lichenoid, ulceration, and edema. Erythema, atrophy, hyperkeratosis, lichenoid, and edema are rated on scales of 0 to 3 (0 = normal/no change, 1 = mild, 2 = moderate, and 3 = severe change). Ulceration and pseudomembrane are rated on scores based on estimated surface area involved (0 = none,  $1 = \ge 0$  but  $\le 1$  cm^2,  $2 = \ge 1$  cm^2 but  $\le 2$  cm^2, and  $3 = \ge 2$  cm^2). The item pool consists of 91 items for 13 areas of the mouth that are assessed for several types of changes. The score is obtained by summing the scores of all items on the OMRS to yield a total possible score ranging from 0 to 273.

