## 6.2 ORAL GVHD SEVERITY SCALES

The primary endpoint will be evaluated using expanded oral GVHD severity scale (**Appendix** A). There is no standard definition of response in this field. The definitions we will use in this pilot study to grade the level of response to study intervention will be as follows:

- **Progression (PD):** defined as increase of 25% of initial score (rounded to the closest number) on the OMRS scale (Appendix A).
- **Partial Response (PR):** defined as decrease of 25% of initial score (rounded to the closest number) on the OMRS scale (**Appendix A**).
- Complete Response (CR): defined as score of 0 on the erythema and ulceration components of the OMRS scale (Appendix A).
- Stable Disease (SD): does not meet criteria for progression or response.

For the purpose of OMRS instrument evaluation validation, we will also use a simplified scale developed for assessment of cGVHD response in the oral cavity (Appendix B). Scoring will be performed by investigators trained in assessment of oral cavity lesions. As part of the evaluation

of the scales, the results will be correlated with scores from symptom-oriented instruments and global scale.

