This study will aim to enroll a total of 34 evaluable patients randomized in a 1:1 fashion (17 per arm) to receive clobetasol rinse or placebo. The initial phase of the study will involve two weeks of either clobetasol rinse or placebo. At the end of the initial 2 weeks, patients receiving placebo will receive 28 days of clobetasol while those receiving clobetasol initially will receive an additional 14 days of clobetasol. Thus, each group will receive 28 days of clobetasol following either a 14 day placebo or immediately after randomization.

Patients will be randomized with a single stratification factor to try to ensure a balanced distribution among those getting placebo or not initially: being identified as having a high intensity of immunosuppression (2 or more agents/modalities  $\pm$  prednisone $\geq$ 0.5 mg/kg/day) vs. no or a lesser intensity of systemic immunosuppression according to the Intensity of Immunosuppression Scale . This scale was developed using expert opinion, and has been preliminarily demonstrated to have predictive validity as measure of the intensity of systemic immunosuppression. A low intensity regimen is defined as treatment with prednisone alone at a dose of less than 0.5 mg per kilogram per day. Moderately intense regimens include single agent prednisone at a dose greater than or equal to 0.5 mg per kilogram per day, and/or any other single agent or modality. Regimens comprised of two or more agents or modalities (+/- prednisone greater than or equal to 0.5 mg per kilogram per day), are categorized as highly intensive systemic immunosuppression. When scoring the intensity of systemic immunosuppression, the use of topical agents is not captured.

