The primary endpoint is the fraction of subjects who experience a 25% improvement in their OMRS compared to their own baseline. The fraction will be estimated with a two-tailed 95% confidence interval as the primary outcome. This will be done using all 34 patients together provided that the changes from baseline to day 28 for the two groups are sufficiently similar. A formal test will be performed assess their comparability. This will be determined conservatively, by obtaining the actual difference in the individual OMRS for each patient at baseline (day 0 for initial clobetasol and day 14 for those initially given placebo) vs. the value after day 28 of clobetasol and comparing those differences between the two randomized groups using a two-tailed Wilcoxon rank sum test. If the p-value for that comparison is >0.30, then the two groups will be considered sufficiently similar to allow pooling of the results and to report a combined

fraction of patients who have a 'response' to 28 days of clobetasol. In this case 34 patients will be sufficient to allow the proportion of patients with a response of 75% or more to have a two-sided 95% confidence interval of +/- 15% or less, which will be considered sufficiently precise. Fractions of responses <75% would have slightly wider confidence interval widths.

An important secondary endpoint is to compare the changes from day 0 in the OMRS until day 14 between those who only receive placebo by that point vs. those who received clobetasol. This evaluation will be done both with respect to the fraction with a response by 2 weeks, as well as comparing the actual changes in OMRS from day 0 to day 14.

By enrolling 17 patients per arm, a 0.10 alpha level one-tailed Fisher's exact test will have 80% power to detect a difference between a potential 75% of patients having a 25% or greater decrease in severity score on the clobetasol arm and about half that amount, 35%, on the placebo arm. A one-tailed test is sufficient for this secondary objective in this study since we will not expect clobetasol to be associated with a lower fraction of patients with benefit compared to placebo and because this is intended to be a pilot study to determine if a potential trend of magnitudes anticipated, but not necessarily a statistically significant gain, may be detected. Should very promising results be obtained, then a subsequent trial could be conducted to build upon and further confirm the benefit noted.

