A comparison of the actual levels of changes in the oral severity score between the arms will also be done using a Wilcoxon rank sum test as a secondary analysis. With 17 patients per arm, there is approximately 80% power to detect a difference between the arms in the changes from baseline to day 14 equal to one standard deviation of the change (effect size=1.0), using a two-tailed Wilcoxon rank sum test with a 0.05 significance level.

All patients will be placed on clobetasol for one month, whether following a two-week period with placebo or beginning at the time of randomization. In addition, comparisons between actual oral severity scores at the beginning of this period and one month later will be made using a paired t-test, or using a Wilcoxon signed rank test if the differences are not normally distributed (p<0.05 by Shapiro-Wilks test). These results will be evaluated separately according to the randomized treatment arm as well as overall if the changes in score according to the randomized assignments are similar (p>0.30 for Wilcoxon rank sum test comparing changes in scores between the two arms over the one month clobetasol period). Although this would also be considered a secondary evaluation, there would be 82% power to identify a 0.75 standard deviation change to be significant with a two-tailed 0.05 alpha level paired t-test if all 17 patients are available within each arm for this comparison.

Patients will undergo oral mucosa biopsies at the beginning of the study, and many are expected to have biopsies at the end of 28 days of treatment. Although required, these biopsies may not be obtained on all patients, and the number of patients with paired data will determine the differences in immunologic parameters from the biopsies that can be detected. For example, if there were 20 patients with paired biopsy data and 5 immunologic parameters of interest, each one would have 93% power to detect a change with an effect size of 1.0, with a very conservative two-tailed 0.01 significance level, to account for multiple comparisons. Fewer than 20 patients with paired biopsies would reduce the power accordingly, but since this is a secondary objective, the results of these tests will be presented in the context of an exploratory study.

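### The randomised day-14 OMRS comparison ignores the randomisation stratum and uses day-0 OMRS only by subtraction; a prespecified rank ANCOVA could gain several power points at a risk of about 1.

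*Combined protocol and SAP*

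**What the plan says.** Sections 2.4 and 10.2 stratify randomisation by one two-level factor, high against no or lesser systemic immunosuppression. Section 10.2 gives the purpose: "Patients will be randomized with a single stratification factor to try to ensure a balanced distribution among those getting placebo or not initially".

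For the blinded fortnight, Section 10.2 names an important secondary endpoint with two parts. One is the fraction responding by two weeks, tested with a one-tailed Fisher's exact test. The other is "comparing the actual changes in OMRS from day 0 to day 14". For the second part, the comparison of "changes in the oral severity score between the arms will also be done using a Wilcoxon rank sum test", two-tailed at 0.05. The plan states about 80% power with 17 patients per arm for a difference of one SD of the change. Neither part uses the stratum, and day-0 OMRS enters the continuous comparison only through the subtraction.

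The nearest text on covariates is general. Section 4.1 says confounders such as changes in immunosuppressants will be considered in the final analysis. Section 2.4 says the same of other medication changes and adds that a small pilot is unlikely to account for every confounder. Neither gives a method or names day-0 OMRS or the stratum as an adjustment.

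**The concern.** After day 14 every patient receives clobetasol, so days 0 to 14 supply the only randomised, placebo-controlled evidence in the trial. With 17 per arm, precision obtained without extra patients is worth having.

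The stratum was judged important enough to be the single stratification factor, yet no analysis uses it. Day-0 OMRS is also likely to matter. Entry requires a score of at least 20, and the items are summed "to yield a total possible score ranging from 0 to 273". Partial response is "defined as decrease of 25% of initial score (rounded to the closest number) on the OMRS scale", so the plan itself treats change as relative to the starting score. A 25% fall is 0.25 × 20 = 5 points for a patient starting at 20 and 0.25 × 80 = 20 points for one starting at 80. If patients change roughly in proportion, the spread of starting scores adds noise to the raw point changes that the Wilcoxon test ranks.

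**Working it through.** **Inputs from Section 10.2:** 17 per arm, two-sided alpha 0.05, effect 1.0 SD of the change, stated power about 80%.

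**The plan's figure.**
- Noncentrality for a two-sample t test: √(17/2) × 1.0 = 2.915.
- Normal approximation: Φ(2.915 − 1.960) = 83.0%. Noncentral t on 32 df: 80.7%.
- Wilcoxon efficiency 3/π: 17 × 0.955 = 16.23 per arm, giving 78.8% by noncentral t.
- Simulated Wilcoxon test (20,000 trials): 78.5%.

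The stated figure is about right.

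**Why a covariate can help.** Let r be the day-0/day-14 correlation and k the ratio of the day-14 SD to the day-0 SD. In units of the day-0 variance, the change has variance 1 + k² − 2rk. After linear adjustment for day 0 the residual variance is k²(1 − r²). With equal SDs the ratio of the second to the first is (1 − r²)/[2(1 − r)] = (1 + r)/2, that is 0.75, 0.85, 0.90 and 0.95 at r = 0.5, 0.7, 0.8 and 0.9. When k = 1/r the ratio is 1: change is unrelated to baseline and adjustment gains nothing.

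**Simulated power.** The rank ANCOVA regresses ranks of the change on arm, ranks of day-0 OMRS and stratum, with a t test on 34 − 4 = 30 df. There were 20,000 trials per setting (40,000 for the prognostic-stratum rows). All values of r, k, tails, skew and stratum effect are assumptions. The stratum is non-prognostic unless stated.

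| Setting | Wilcoxon | Rank ANCOVA |
|---|---|---|
| Normal, k = 1, r = 0.3 | 78% | 90.5% |
| r = 0.5 | 78-79% | 87% |
| r = 0.7 | 78-79% | 83% |
| r = 0.8 | 78-79% | 81% |
| r = 0.9 | 78-79% | 79-80% |
| r = 0.95 | 78.1% | 78.0% |
| k = 0.8, r = 0.5 to 0.9 | 78-79% | 91-93% |
| k = 1.2, r = 0.5 to 0.9 | 78-79% | 78-82% |
| k = 1.43, r = 0.5 to 0.9 | 78-79% | 77-84% |
| Change unrelated to baseline (k = 1/r) | 78% | 77% |
| Same, t(5) changes | 86.0% | 85.2% |
| Same, t(3) changes | 94.5% | 94.1% |
| Stratum shifts change 0.5 SD; r = 0.7, k = 1 | 78.7% | 85.0% |
| Stratum shifts change 0.5 SD; k = 1/r | 78.8% | 79.9% |

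**Skewed scores, proportional change.** Day-0 scores are lognormal (median 30 or 40, log-SD 0.4 or 0.5) truncated at 20, and day-14 scores are capped at 273. The mean log ratio is set so that 35% on placebo and 75% on clobetasol fall by at least 25%, the response rates Section 10.2 uses for the Fisher test.

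| SD of log ratio | Wilcoxon | Rank ANCOVA |
|---|---|---|
| 0.2 | 63-70% | 77-79% |
| 0.3 | 70-76% | 78-80% |
| 0.45 | 74-77% | 78-79% |
| 0.6 | 75-77% | 78-79% |
| 0.8 | 75-77% | 77-78% |

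The 9-14 point gains at SD 0.2 need a particular world. A 35% placebo response puts the mean log ratio at ln 0.75 + 0.385 × 0.2 = −0.288 + 0.077 = −0.211, and exp(−0.211) = 0.81, a median placebo fall of 19%. At SD 0.6 to 0.8 the gain is 1-3 points.

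**Type I error.** Rank ANCOVA: 4.6-5.4% across settings, and 5.0% in runs of 120,000 skewed trials. The unstratified Wilcoxon test becomes conservative, at 4.1-4.2%, when the stratum shifts change by 0.5 SD.

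**Why stay rank-based.** Raw-score ANCOVA loses 3-5 points against the Wilcoxon test at log-ratio SD 0.6, 6-11 at SD 0.8 (with or without the cap), and 6-11 with t(5) or t(3) changes unrelated to baseline. The plan expects a heterogeneous group and, for the paired analysis, already provides for "using a Wilcoxon signed rank test if the differences are not normally distributed".

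**The case against.** Nothing in the plan is wrong: the Wilcoxon test is valid, its power is as stated, and stratification was introduced for balance. The trial is a pilot whose primary outcome is a response fraction with a confidence interval. Section 10.2 says it seeks a trend rather than necessarily a significant gain, so a few power points on a companion secondary test alter no stated decision. Section 2.4 signals modest ambitions for adjustment. All of that stands, and it limits the point to an optional improvement.

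The gain also depends on inputs nobody has. Two assessments 14 days apart may correlate highly, and with equal SDs the gain is then close to nil. This stands too; the case rests on the asymmetry between a loss of about 1 point and possible gains of several.

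The strongest objection concerns the method. If change really is proportional, ranking percentage change needs no covariate and does better: 82-83% power in the skewed settings against 77-79% for rank ANCOVA in the same runs. But percentage change loses about 2-4 points against the raw-change Wilcoxon test when changes are additive and unrelated to baseline. It also leaves the stratum unused and replaces the plan's endpoint. Rank ANCOVA keeps the endpoint and risks less.

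Finally, several results from 34 patients can disagree. In the skewed runs, the Wilcoxon test and rank ANCOVA differed on significance in 6-19% of trials, and rank and raw ANCOVA in 9-15%. That is a real interpretive cost, and the reason to fix in advance which one is the test.

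**Conclusion.** The point holds as a missed efficiency in one secondary analysis. The only placebo-controlled comparison of OMRS change leaves two collected variables unused. Adjusting for both by rank ANCOVA risks about 1 power point if neither is prognostic. With equal SDs it gains about 8 points at a correlation of 0.5, 4 at 0.7, 3 at 0.8 and about 1 at 0.9. Under skewed, proportional change it gains between 1 and 14 points, the top of that range only when the log-ratio SD is 0.2. These are ranges over assumed inputs, so confidence in the size of the gain is moderate. The responder comparison by Fisher's exact test is not in question.

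**What to change.** Before day-14 OMRS is compared by arm, amend Section 10.2 as follows.

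- Make a rank ANCOVA the test for the continuous day-14 comparison: ranks of the day 0 to 14 change in OMRS (mid-ranks for ties), regressed on arm, ranks of day-0 OMRS and immunosuppression stratum (high or not high), two-sided 0.05.
- Rank the change, not the day-14 score. Ranking the day-14 score gives 76.1%, 71.1% and 66.0% power at correlations of 0.8, 0.9 and 0.95, against about 78% for the planned test.
- Always report the unadjusted Wilcoxon test beside it, with no choice between the two after seeing the data.
- Report an ANCOVA-adjusted difference in OMRS points with a 95% CI, as a supporting estimate only.
- Leave the one-tailed Fisher test as planned.

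The cost is SAP wording, since both covariates are already collected (Appendices G and H). The downsides are two degrees of freedom, the 1-point risk, a t-based rather than exact p-value, a rank coefficient that is not in OMRS points, and the need to explain any disagreement between the reported results.

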## **3** STUDY IMPLEMENTATION

## 3.1 STUDY DESIGN

This is a randomized, double blind, placebo-controlled, pilot study of clobetasol 0.05% topical oral rinse with an open label cross-over or extension period. Consenting subjects with clinically significant oral chronic GVHD will be randomized to clobetasol 0.05% or placebo oral rinse. The placebo will be flavored with quinine, to approximate the "bitter" taste of clobetasol.

Subjects will be evaluated at bi-weekly intervals while on the study intervention. OMRS score will serve as the primary outcome measure. At the first 2 week interim appointment patients will be unblinded and started on the clobetasol oral rinse open label. In the absence of progressive oral disease on the scheduled interim evaluations during the 4-week clobetasol treatment period, all patients will complete a total of 4 weeks of treatment with clobetasol. Therefore, patients who were originally assigned to clobetasol arm will receive additional 2 weeks of treatment, and patients assigned to placebo arm will undergo an additional 4 weeks of treatment with clobetasol after unblinding. Patients with progressive disease after 2 weeks of therapy with clobetasol will be considered non-responders, taken off-treatment and treated as appropriate in consultation with primary clinician. Within 90 days of the end of the 1 month of treatment, all patients with evidence of benefit (response or stable disease) will be given an option to continue treatment with clobetasol 0.05% with or without additional treatment as deemed clinically necessary for 1 month after the conclusion of the initial treatment period. Additional follow-up appointment will be scheduled for all patients 1 month after completion of treatment. The change in OMRS scores from baseline to 4 weeks of mouth rinse usage will be the primary outcome variable. For the placebo group, the OMRS score at the end of the blinded phase/beginning of clobetasol rinse use (day 14) will serve as the baseline for the primary outcome. Difference in OMRS score between the groups (placebo and clobetasol) at the end of the 14-day blinded phase will serve as a secondary outcome measure. The study schedule of events is outlined in Appendix G.

# 

#	Because of problems with your teeth, denture or mouth have you	Never (0)	Hardly ever (1)	Occasionally (2)	Often (3)	Very Often (4)
1	Had trouble pronouncing words					
2	Felt sense of taste has worsened					
3	Had painful aching in the mouth					

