## **10.2** STATISTICAL CONSIDERATIONS

The primary objective of this randomized pilot study is to determine if the use of clobetasol may result in improvement or stabilization in outcomes in patients with oral chronic GVHD. An important secondary objective is to preliminarily validate and explore the utility of the response measurement instruments.

Patients with oral cGVHD meeting the eligibility criteria will be separately randomized to either 1 month of clobetasol 0.05% oral rinse or placebo; there will not be separate accrual goals for each age group or type of underlying disease. The patients will be followed every 2 weeks for 1 month for their primary endpoint, and once 1 month after completion of study agents.

The primary endpoint will be the change in OMRS score (**Appendix A**) after 1 month of clobetasol 0.05% oral rinse compared to baseline. We will consider a 25% or larger decrease in the score to be clinically significant and a 'response' for the purpose of this study. As this is a pilot study, the association between this level of change and other scales will also be assessed to determine if this is a meaningful measure to use in future trials or if modification is warranted. Thus, this study will be a pilot for the determination of a meaningful response as well for determining if the agent tested may be beneficial.

After the first 2 weeks of clobetasol treatment, patients can be removed from study if oral disease progression is documented. Patients who are taken off study for oral disease progression will be counted as non-responders at the time of the final analysis. Patients taken off study for non-compliance, specifically  $\geq$ 75% non-use of the oral rinse, will not be included in the data analysis

The patients enrolled on this study may be a very heterogeneous group with respect to prior treatments, extent of disease, etc. Patients taken off study for reasons unrelated to the primary outcome will be classified as non-responders and analyzed accordingly. The results will be interpreted in the context of a pilot study with potential limitations noted.

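### Section 10.2 gives no OMRS value for patients stopped for progression at 2 weeks of clobetasol, so as written they leave the 28-day change analyses because they worsened

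*Combined protocol and SAP*

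**What the plan says.** Section 3.1 sets the stopping rule: "Patients with progressive disease after 2 weeks of therapy with clobetasol will be considered non-responders, taken off-treatment and treated as appropriate". Section 10.2 repeats it more loosely ("After the first 2 weeks of clobetasol treatment, patients can be removed from study if oral disease progression is documented") and gives the consequence for response: "Patients who are taken off study for oral disease progression will be counted as non-responders at the time of the final analysis". Section 6.2 defines progression as a 25% rise in OMRS from the initial score.

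Two analyses in 10.2 use the size of the OMRS change over the clobetasol month rather than response:

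- The test that decides whether the arms may be pooled takes each patient's score at the start of clobetasol against "the value after day 28 of clobetasol and comparing those differences between the two randomized groups using a two-tailed Wilcoxon rank sum test". Pooling is allowed if p>0.30.
- A secondary analysis within each arm, and overall if the arms are similar: "comparisons between actual oral severity scores at the beginning of this period and one month later will be made using a paired t-test". The signed rank test is the fallback. Its 82% power for a 0.75 SD change holds "if all 17 patients are available within each arm for this comparison".

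Section 3.3.3 asks for the full end-of-treatment evaluation, OMRS included, at day 28 or, where possible, whenever a patient comes off treatment. Neither 3.3.3 nor 10.2 says that this score stands in for day 28.

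**The concern.** A patient who progresses at 2 weeks stops then, and by design has no on-treatment score at day 28. The non-responder rule settles that patient's place in the responder fraction. It supplies no number, rank or imputation for a t-test or a rank sum test. Taken at its word, the text drops the patient from both.

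The loss is not random: these patients are missing because their OMRS rose by at least a quarter. Leaving them out makes the mean change look better unless the remaining patients worsen as much. The test that permits pooling would also ignore patients whom the pooled fraction then counts as failures. With no rule stated, the choice would be made after the data are known.

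**Working it through.** **The plan's own figure.** Paired t-test, n=17, effect 0.75 SD, two-sided 0.05, noncentral t: power 82.7%, which agrees with the stated 82%. With 16, 15 or 13 patients per arm it is 80.1%, 77.1% or 70.0%. The stated figure is right for the condition it names.

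**Direction, by arithmetic.** Suppose the other patients improve by 12 points on average and one patient stops at +7 (25% of an assumed baseline of 28).
- n=34: (33×12 − 7)/34 = 11.44; leaving the patient out gives 12.0, which is 4.9% too high.
- n=17: (16×12 − 7)/17 = 10.88; leaving the patient out gives 12.0, which is 10.3% too high.

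**Size, with assumed inputs.** From the plan: 17 per arm, 75% response, and 25% thresholds for response and progression. Assumed, because the plan gives none of them: baseline 28, SD of change σ = 8 or 12, normal changes at weeks 2 and 4 with correlation ρ = 0.7, and the same mean m at both weeks (negative means improvement).

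- A 75% response fixes m: m = −(7 + 0.674σ), so −12.4 (σ=8) or −15.1 (σ=12).
- A patient stops if the week-2 change is +7 or more. With z = (7 − m)/σ, the expected number stopped is 34 × [1 − Φ(z)].
- Leaving them out shifts the week-4 mean towards improvement by ρσφ(z)/Φ(z), compared with everyone continuing treatment.
- Using the score at stopping shifts it the other way, by (1 − ρ)σφ(z).
- The gap between the two rules is the sum.

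| Setting | z | Stopped, of 34 | Omission shift | Stop-score shift | Gap (points) |
|---|---|---|---|---|---|
| 75%, SD 8 | 2.42 | 0.26 | 0.12 | 0.05 | 0.17 |
| 75%, SD 12 | 1.84 | 1.1 | 0.64 | 0.26 | 0.90 |
| No change, SD 8 | 0.875 | 6.5 | 1.88 | 0.65 | 2.5 |
| No change, SD 12 | 0.583 | 9.5 | 3.93 | 1.21 | 5.1 |

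**Effect on the tests**, by simulation of the same model:

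- 75% response: the by-arm paired test is significant in essentially every trial under either rule; the conclusion differs in 0% (SD 8) or 0.4% (SD 12). The pooling decision differs in 3% or 10% of trials, but 70–72% of trials pool under every rule.
- 50% response, SD 8: about 1.4 patients stopped and a gap of about 0.7 points. Significance is 96% with them left out and 88% with stop scores, against about 92% if all had continued.
- No true change: significant improvement per arm in about 14% (SD 8) or 21–22% (SD 12) of trials with these patients left out (13–22% over repeated runs), against a nominal 2.5%. With stop scores it is about 1%.

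**Sensitivity.** If only half the effect is present at week 2 (75% response, SD 8), about 1.7 patients stop and the gap is 1.15 points; the by-arm conclusion changes in 0.4% of trials (5% at SD 12). A separate calculation on percentage change (SD 20–40, correlation 0.5–0.8, no true change) gives 6–27% false improvement per arm with omission, and at most 2.1% with stop scores.

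**The case against.** Four points count against the concern.

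- **The wording can be read otherwise.** The word for actual scores may only contrast raw scores with the dichotomised response. The pooling paragraph speaks of a difference for every patient and of all 34 together. The clause on 17 available patients is a power condition, not an exclusion rule. Section 3.3.3 files the stop-visit assessment under the same evaluation as day 28, so using it is a natural reading. This stands as far as it goes, but no value is actually named for a stopped patient.
- **The effect is small where the plan expects to be.** This stands. At 75% response it is a fraction of a point and the test conclusions hold.
- **The stop score has its own bias.** It is a 14-day value in a 28-day comparison. In the 50%, SD 8 case, omission and stop score miss the continued-treatment result by similar amounts in opposite directions. This stands too; the case for the stop score is that it errs against the drug.
- **The primary endpoint is safe.** A reader might infer that it is biased, since 3.1 says "The change in OMRS scores from baseline to 4 weeks of mouth rinse usage will be the primary outcome variable" and 10.2 opens with "The primary endpoint will be the change in OMRS score". The documents do not support that. Section 10.2 goes on to make the responder fraction with its confidence interval the primary outcome, 1.2.4 does likewise, and 10.2 labels the paired comparison secondary. Patients who progress are already failures in that fraction.

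A reader might also infer that the pooling test is pushed towards pooling, or that off treatment in 3.8.1 contradicts off study in 3.8.2. The first is not borne out: decisions differ in single trials, without direction. The second fails because the two lists serve different purposes.

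**Conclusion.** The gap is real and confined to the secondary paired comparison and the rank sum test that decides pooling. Followed literally, 10.2 removes patients from both because they worsened, and the reported change then favours clobetasol. That direction follows from the stopping rule, unless the remaining patients worsen as much.

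The size does not follow from the documents, which give no SD, baseline or progression rate. Under the assumptions shown, it is 0.2 to 0.9 points at the planned response with almost no change in conclusions. It becomes serious only if the drug does little: a false per-arm improvement rate of about 13–22% instead of about 2.5%. A pilot should be able to recognise that case. This is a low-priority clarification, worth making because it is cheap.

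**What to change.** Add one sentence to 10.2: for patients stopped for oral progression, the OMRS at stopping (from the 3.3.3 evaluation, or from the visit that documented progression) is the end-of-treatment value in both the paired comparison and the rank sum pooling test, with worst rank as a sensitivity analysis.

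No new visit or measurement is needed, because progression is itself diagnosed from an OMRS. The price is that a 14-day value enters a 28-day comparison, so the estimate is conservative and the reported change less favourable. At a true mean change of −15% in the percentage-change calculation, the rule reports −8% to −14%, against −16% to −27% with these patients left out. The report should state this alongside the result.
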